1. INTRODUCTION: BACKGROUND AND SCIENTIFIC RATIONALE

1.1. Background Information

Botanix Pharmaceuticals' BTX 1204 contains the active pharmaceutical ingredient, cannabidiol (CBD; *2-[(1R,6R)-6-isopropenyl-3-methylcyclohex-2-en-1-yl]-5-pentylbenzene-1,3-diol*). CBD is a member of a broader family of compounds known as cannabinoids, a class of compounds originally derived from the *cannabis sativa* plant. [Olah 2014] CBD is chemically synthesized under Good Manufacture Practices (GMP) for use in this study.

Interest in CBD-based therapeutics has increased significantly in recent years, as published data has highlighted the potential efficacy and safety benefits of this compound. [Volkow 2015] CBD is not psychoactive and clinical trials have demonstrated that CBD may successfully treat epilepsy, arthritis, pain, and even Fragile X Syndrome. [Fernandez-Ruiz 2012] There are now more than 150 human clinical trials that have been completed, are underway, or pending recruitment around the world that are studying CBD in a range of diseases. [ClinicalTrials.gov Aug 2018]

Botanix Pharmaceuticals is developing a number of topical formulations aimed at exploiting the potential immune regulatory and anti-inflammatory effects of CBD that have reported in the literature. Initial clinical development of these topical formulations has focused on establishing the safety and local cutaneous tolerability when applied to the skin of healthy volunteers either as a single dose or as multiple doses. Subsequent clinical studies have again focused on establishing safety and local cutaneous tolerability in the disease state under investigation. To date, Botanix Pharmaceuticals has completed 3 Phase 1 clinical studies with formulations containing concentrations of CBD up to 5% (w/w) with once (QD) or twice daily (BID) dosage regimens for up to 28 days. These formulations have been well-tolerated on normal skin and on skin displaying the underlying pathology of acne or atopic dermatitis (AD). In the most recent study, 37 subjects with mild to moderate AD were treated with either vehicle or BTX 1204 4% (w/w) BID for 28 consecutive days. Evidence of a potential therapeutic benefit of BTX 1204 over vehicle was observed through at reduction in the Signs of AD scores from Baseline.

This study is intended to establish safety, tolerability and efficacy in subjects with moderate AD treated BID with BTX 1204 4% (w/w) Liquid Formulation compared to subjects treated with Vehicle for 12 weeks.

1.2. Rationale

1.2.1. Pathogenesis of Atopic Dermatitis

Atopic dermatitis is an inflammatory cutaneous disease which may co-exist with other immunoglobulin E (IgE)-dependent atopic diseases such as allergic rhinitis, bronchial asthma, and food allergy. [Nowicki 2015] The disease is a skin disorder which presents itself as itchy, inflamed, red, and possibly lichenified (*i.e.* thickened) skin with affected areas potentially distributed widely over the body. [National Eczema Organization, 2017] The pathogenesis of the disease is thought

to involve an acute T-helper 2 (Th2) cell response followed by a chronic response involving additional T-helper populations; although more recent research suggests that Th2 cells and a more generalized T-cell response are present during both acute and chronic phases. [Gandhi 2017] The importance of Th2 cells and interleukin (IL)-4 and IL-13 signaling in the disease is supported by the effectiveness of dupilumab, a human monoclonal antibody specific to IL-4R α that can block IL-4 and IL-13 signaling, to improve many symptoms of AD including pruritus, and reduction in AD area and severity. [Gandhi 2017]

The classical steps of AD pathogenesis are the following (Figure 1):

- A skin barrier defect or entry of a skin irritant triggers the release of IL-25, IL-33, and thymic stromal lymphopoietin (TSLP) from keratinocytes, which activate dendritic cells (antigen-presenting cells in the skin) and Langerhans cells.
- During the “acute phase” of onset, dendritic cells cause excessive Th2, T-helper 22 (Th22), and T-helper 17 (Th17) cell activation (note that these changes continue into the “chronic phase” of the disease).
 - Th2 cells produce IL-4, IL-13, and IL-31, which then induce changes in keratinocyte gene expression, disrupt skin barrier function, and trigger itch symptoms. IL-4 and IL-14 can increase additional TSLP release from keratinocytes, which causes further Th2 cell activation.
 - Activated Th22 cells release IL-22 which promotes keratinocyte hyperplasia, downregulates keratinocyte differentiation, and synergizes with IL-17 to induce pro-inflammatory S100 genes.
 - Activated Th17 cells release IL-17 which can regulate S100 protein and gene expression.
- During the chronic stage (day 3 onward), dendritic cells recruit T-helper 1 (Th1) cell populations *via* IL-12 and continue to recruit Th22 and Th17 cells. Th1 cells release interferon- γ (IFN- γ), which may decrease the role of Th2 cells in the disease. Th1, Th22, and Th17 cells induce responses that continue to attract additional immune cells to the epidermis, alter keratinocyte differentiation, and induce epidermal thickening.

Figure 1 Pathogenesis of Atopic Dermatitis

[figure not shown]

Figure 1 provides the various pathways involved in atopic dermatitis (from Guttman-Yassky 2017). DC = dendritic cell; IFN- γ = interferon- γ ; IL = interleukin; KC = keratinocyte; LC = Langerhans cell; Th = T-helper; TSLP = thymic stromal lymphopoietin

It is estimated that Th2 cell response is dominant in ~80% of AD cases (extrinsic AD), but in other instances (intrinsic AD), there is a shift to a more pronounced Th22 and Th17 response. [D'Erme 2017] A recent study suggests that IL-17 may have a more dominant role in AD than proposed in classical models [Tan 2017]:

- Compared to healthy children, IL-17 protein levels were elevated in AD skin lesions, but not in the serum of children with AD, indicating that IL-17 acts locally.
- The effects of 2,4-dinitrochlorobenzene (DNCB; used to induce a model of AD in mice) were evaluated in IL-17 knockout and in wild-type C57Bl/6 mice. DNCB was able to induce AD-like lesions in both types of mice; however, epidermal and dermal thickness of the lesions in the IL-17 knockout mice were significantly decreased compared to what was observed in wild-type mice.
- Skin mRNA levels of the Th2 cytokines IL-4 and IL-13 were decreased in IL-17 knockout mice compared to wild-type mice; however, there was no difference in skin mRNA expression levels of IFN- γ . Splenocytes isolated from naïve IL-17 knockout mice released less IL-4 following concanavalin A (ConA) stimulation (a model of T-cell activation) compared to splenocytes from treated wild-type mice.

IL-17 has been shown to trigger a pro-inflammatory response in an immortalized human keratinocyte cell line (HaCaT cells). The addition of IL-17 increased the release of pro-inflammatory IL-6 and IL-8, but not IL-1 β . This suggests that IL-17 may play a key role in the immune response associated with AD.

1.2.2. Rationale for the Development of BTX 1204 for the Treatment of Atopic Dermatitis

The published literature suggests that CBD can potentially address the underlying immunological pathways and inflammatory response associated with AD. CBD has been shown to alter gene expression of antigen-primed T-cells to induce a state of anergy *via* the Erg2 pathway and induce gene expression changes that leads to decreased antigen recognition in B-cells in an autoimmune disease model with a predominant Th17 response. [Kozela 2015] This suggests that CBD was able to decrease primed T-cell activity and also inhibit subsequent B-cell response. CBD also altered gene expression in gingival stem cells to reduce antigen expression, thereby decreasing the potential for these cells to initiate an autoimmune response (Libro 2016), which could also provide a rationale for the use of CBD as a possible therapy for GvHD. [Yeshurun 2015a, Yeshurun 2015b] CBD was also shown to suppress multiple T-cell populations and inhibit general T-cell activation. [Faubert Kaplan 2003, Ignatowska-Jankowska 2009] Numerous experimental models have indicated that CBD can decrease concentrations of pro-inflammatory mediators and also increase the release of anti-inflammatory cytokines (such as IL-10). CBD has also been shown to directly inhibit inflammatory responses due to the addition of IL-17A or IFN- γ . [De Filippis 2011, Harvey 2014] The potential for CBD to inhibit the effects of IFN- γ and/or decreasing IFN- γ levels could serve a dual purpose; lower levels of IFN- γ could translate to a decreased inflammatory response and improve skin barrier function by reducing IFN- γ -mediated inhibition of long-chain fatty acid ceramide production in the skin. [Tawada 2014]

Importantly, the literature indicates that CBD can inhibit the migration, proliferation and cell maturation processes involved in Th17, Th1, and Th2 immune responses. [Kozela 2015, Kozela 2016, Lee 2016] These are considered critical immune pathways involved in the pathophysiology of AD. [Guttman-Yassky 2017] CBD may have beneficial effects on AD due to direct antioxidant effects, and ability to improve antioxidant status in models of inflammation and autoimmune disease. [Ben Shabat 2006, Booz 2011, De Filippis 2011, Fouad 2011, Mukhopadhyay 2011, Fouad 2012, Giacoppo 2015, Lee 2016] Finally, CBD may also provide a therapeutic benefit for the treatment of AD by modulating the inflammatory response regulated by keratinocytes. CBD inhibited the production of monocyte chemotactic protein-2 (MCP-2), IL-6, IL-8, and tumor necrosis factor- α in polyinosinic-polycytidylic acid stimulated human keratinocyte (HaCaT) cells. [Petrosino 2018] CBD has also been shown to directly inhibit the proliferation of keratinocytes. [Wilkinson 2007]. The potential mechanisms for CBD activity in AD are listed in **Table 1**.

Table 1 Potential Mechanisms of Cannabidiol as a Treatment for Atopic Dermatitis

Atopic Dermatitis

- Decrease differentiation and proliferation and activity of t-helper 1, 2, and 17 cells.
- Decrease interferon- γ and IL-17 levels and downstream effects.
- Decrease interferon- γ , which may have an inflammatory effect and improve ceramide production in the skin. The latter may prevent deterioration of skin barrier function.
- Decrease monocyte chemotactic protein-2 (MCP-2), IL-6, IL-8, and tumor necrosis factor- α .
- Decrease keratinocyte proliferation.
- Increase intracellular expression of antioxidants and decrease reactive oxygen species.

It should be noted that there were no publications evaluating the effects of CBD on AD in the clinic or in animal models of this disease. Additionally, there were no publications identified that explored the effects of CBD on the Th22 cell pathway.

While CBD did appear to have a consistent anti-inflammatory and autoimmune inhibitory effect in the identified publications, some caution is warranted when trying to evaluate the potential effects of CBD for AD based on data from different autoimmune inflammatory disease models, as the underlying cause of the diseases models could differ. For example, CBD had definitive effects on inhibiting IL17 release, decreasing Th17 cell activity and gene expression activity in an *in vitro* model of autoimmune encephalitis; however, CBD did not have any effects on antigen-mediated TNF- α or INF- γ release in this same model. [Kozela 2013, Kozela 2015, Kozela 2016] Similarly, in a murine model of type 1 diabetes, CBD was reported to inhibit Th1-mediated autoimmunity, but shift an immune response towards Th2 immunity, which was considered beneficial for the disease. [Weiss 2008] It is unclear whether CBD would induce a shift in T-cell populations in AD. Although there were subtle differences in how specific pathways were affected by CBD in these models, overall, CBD did demonstrate notable effects on inhibiting autoimmune responses in the test systems evaluated.

An additional consideration needs to be given to a specific mechanism of action for CBD. While not thoroughly investigated in each case, many of these studies showed that the reported effects of CBD are likely to be independent of cannabinoid receptors (CB₁ or CB₂). Additional receptors that could be involved with CBDs effects on immune response and inflammation could be peroxisome proliferator-activated receptors (PPARs), adenosine A₂ receptors, or the transient receptor potential cation channel subfamily V1 (TRPV1). [De Filippis 2011, Esposito 2011, Hegde 2011, Ribeiro 2012, Petrosino 2018] However, the involvement of specific receptors is likely different for each model of autoimmune inflammation.

1.2.3. BTX 1204 Nonclinical and Clinical Data

The safety of BTX 1204 is supported by information from the published literature and studies conducted by Botanix Pharmaceuticals. Botanix Pharmaceuticals has conducted nonclinical and clinical studies with CBD and with CBD formulated in an almost identical siloxane-based formulation known as BTX 1503. The only difference between these formulations is that BTX 1503 contains a very small amount of polydimethylsiloxane (dimethicone) at 1.0% (w/w). Comparative *in vitro* biopharmaceutic studies have shown both formulations have comparable transdermal permeation rates and equivalent deposition into the epidermal and dermal skin layers.

To date, Botanix Pharmaceuticals has performed a full battery of genotoxicity studies, an ocular irritation study, a single dose pharmacokinetic (PK) study in minipigs, a 28-day repeat-dose oral toxicology study in rats, 28- and 90-day dermal toxicology studies in minipigs, and a local lymph node assay (LLNA) that support the safety of BTX 1204. In addition, nonclinical information on systemic exposure to CBD obtained from the published scientific literature on the efficacy and safety pharmacology, on PK and metabolism, and on toxicity support the safety of CBD.

The results from these studies along with a comprehensive review of the scientific literature has established the safety profile of CBD and supports the proposed clinical investigation (BTX.2018.003) with topical application of CBD to patients with AD. Details on the observations from Botanix Pharmaceuticals' studies and the extensive literature review can be found in the IB.

In addition, to the nonclinical data, the safety and tolerability of BTX 1204 4% (w/w) was evaluated in subjects with mild to moderate AD (BTX.2017.004). In this study, BTX 1204 4% (w/w) Solution or Vehicle was applied to a target AD lesion and surrounding skin BID (180 mg CBD/day) for 28 consecutive days.

Safety was assessed through collection of AEs, laboratory findings (CBC, chemistry, and urinalysis), urine drug tests conducted to detect the presence of THC, signs of AD score on the target lesion (erythema, exudation, excoriation, induration/papulation, and lichenification), and cutaneous tolerability assessments.

This study demonstrated that daily topical treatment of BTX 1204 4% (w/w) Solution BID was safe and well tolerated. No early discontinuations occurred as a result of an AE. There were no SAEs reported and the most common AEs were general disorders and administration site conditions including application site erythema, application site pruritus, and application site pain.

In studies conducted with BTX 1503, a formulation similar to BTX 1204 but with a drug load of 5% (w/w), facial dryness and facial itchiness were reported as possible effects of the study drug treatment in a healthy volunteer study (BTX.2017.001). In an acne study (BTX.2017.002), slight to moderate erythema was reported most frequently in cutaneous tolerability assessments. However, most subjects that reported erythema pre-or post-study drug application had erythema at Baseline and treatment with BTX 1503 did not exacerbate the erythema. Only 1 subject had increased erythema from Baseline and this was reported at Day 35, seven days after their final application of study drug. Slight scaling was reported in 2 subjects (9.5%), slight dryness was reported in 4 subjects (19.0%) and slight burning/stinging was reported in 5 subjects (23.4%). Only one positive cutaneous tolerability assessment (slight dryness) was reported at more than a single visit.

There is adequate support for evaluating the use of BTX 1204 4% (w/w) Liquid Formulation in this clinical study based on the findings observed in nonclinical and clinical studies conducted by Botanix Pharmaceuticals and its active ingredient CBD along with the extensive published literature on the use of CBD in multiple settings.

1.3. Potential Risks and Benefits

1.3.1. Known Potential Risks

Based on studies conducted by Botanix Pharmaceuticals with BTX 1204 4% and similar CBD products, the potential risks associated with BTX 1204 include:

- Ocular irritation
- Local application site AE's
- Cutaneous reactions which may include erythema, dryness, scaling, and burning/stinging.

In the current study, subjects will be allowed to use their usual moisturizers. Subjects in this study will be given instructions on what to do if BTX 1204 liquid accidentally gets into the eyes via a provided "patient instruction" video.

In the published scientific literature, the only target organ for toxicity that has been identified was the testes in rat and monkey studies. It is uncertain if the reduction in spermatogenesis noted in these animal studies has a clinical correlate. In addition, this finding was not observed in the 28-day oral rat study or in the 28- or 90-day dermal minipig studies conducted with Botanix Pharmaceuticals' BTX 1503.

The other aspect of systemic exposure to CBD reported in the published scientific literature was the potential for competitive binding to CYP450 isozymes, indicating a potential for drug-drug interactions. Given the limited systemic exposure observed in Botanix Pharmaceuticals' healthy volunteer study, the potential for a drug-drug interaction is considered to be minimal.

1.3.2. Known Potential Benefits

This study is the second study in evaluating the use of BTX 1204 4% (w/w) in subjects with AD. The preliminary efficacy of BTX 1204 4% (w/w) was evaluated in a Phase 1b, randomized, double-blind, vehicle-controlled study. After only 4 weeks of treatment, subjects receiving BTX 1204 4% (w/w) had improvements in the Signs of AD score compared to treatment with Vehicle. A total of 34.8% of subjects receiving BTX 1204 had a ≥ 4 -point improvement in the Signs of AD score compared to 18.2% of subjects receiving vehicle. Improvement was observed primarily in erythema, exudation and lichenification.

Based on the non-clinical and accumulating clinical data, there is evidence that treatment with BTX 1204 4% (w/w) in subjects with AD may lead to decreased inflammation which may lead to a decrease in the signs and symptoms associated with AD. As with any new form of treatment, potential benefits are not guaranteed. Results from this study will provide guidance for additional safety and efficacy studies in AD and potentially other target patient populations.

2. OBJECTIVE

The objective of this study is to determine the safety, tolerability and efficacy of BTX 1204 4% (w/w) in subjects with moderate atopic dermatitis.

3. STUDY DESIGN AND ENDPOINTS

3.1. Description of the Study Design

This is a randomized, double-blind, vehicle-controlled, Phase 2a study in subjects with moderate AD. Eligible subjects will be enrolled and randomized to treatment with BTX 1204 4% (w/w) or Vehicle for 84 days. Approximately two hundred (200) subjects randomized 1:1 (100 active: 100 vehicle) will be enrolled.

3.2. Study Endpoints

The primary endpoint for the study is the proportion of subjects with an Investigator's Global Assessment (IGA) success defined as an IGA score of "Clear" (0) or "Almost Clear" (1) with at least a 2-grade improvement from Baseline at Day 85.

The secondary endpoints for the study are:

- The proportion of subjects with an EASI 75 score at Day 85,
- The proportion of subjects with an EASI 50 score at Day 85,
- The change from Baseline in the Signs of AD score at Day 85,
- The proportion of subjects with an IGA of Clear or Almost Clear at Day 85,
- The proportion of subjects with at least a 2-grade improvement in ISGA from Baseline at Day 85,
- The change from Baseline in the percent of body surface area (BSA) affected by AD at Day 85,
- The time to achieve IGA success, and
- The change from Baseline to Day 85 in the Itch-Numerical Rating Scale (I-NRS)

Exploratory analyses will be conducted for:

- The change from Baseline in the Signs of Atopic Dermatitis score at Day 15, Day 29, and Day 57,
- The change from Baseline in the percent of body surface area (BSA) affected by AD at Day 15, Day 29, and Day 57,
- The proportion of subjects with IGA success defined as an IGA score of "Clear" (0) or "Almost Clear" (1) with at least a 2-grade improvement from Baseline at Day 15, Day 29, and Day 57,
- The absolute and percent change from Baseline in the Eczema Area Severity Index (EASI) score at Day 15, Day 29, Day 57, and Day 85,

- Change from Baseline in the subject's reports of pruritus obtained daily on a Patient Diary,
- Time to improvement of pruritus (change of ≥ 4 in the Worst Itch Numerical Rating Score [WI-NRS, 0 – 10 score]),
- Subject's assessment of the change in their AD from Baseline to Day 85 (Patient Reported Outcome [PRO]), and
- The change from Baseline to Day 29, and Day 57, and Day 85 in the Signs of AD score for the target lesion (selected sites).

Safety outcome measures to be assessed are:

- Reported adverse events (AEs) including treatment-emergent (TEAE) monitored from time of consent through the end of study,
- Changes in clinical labs including complete blood count (CBC), chemistry, and urinalysis between Baseline and Day 85, and
- Subject's reports of burning/stinging obtained during visits on Day 1, Day 15, Day 29, Day 57, and Day 85.

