The Signs of AD score will be an examination of all lesions on the subject for the presence of erythema, exudation, excoriation, induration/papulation, and lichenification. Each sign will be graded according to the grade and definitions provided in Table 3.

Table 3 Signs of Atopic Dermatitis (Paller)

Score	Grade	Definition
Erythema (redness)		
0	None	No redness
1	Mild	Mildly detectable erythema; pink
2	Moderate	Dull red; clearly distinguishable
3	Severe	Deep, dark red; marked and extensive
Exudation (oozing and crusting)		
0	None	No oozing or crusting
1	Mild	Minor or faint signs of oozing
2	Moderate	Definite oozing or crusting
3	Severe	Marked and extensive oozing or crusting
Excoriation (evidence of scratching)		
0	None	No evidence of excoriation
1	Mild	Mild excoriation
2	Moderate	Definite excoriation
3	Severe	Marked, deep, or extensive excoriation
Induration/papulation		
0	None	None
1	Mild	Slightly perceptible elevation
2	Moderate	Clearly perceptible elevation but not extensive
3	Severe	Marked and extensive elevation
Lichenification (epidermal thickening)		
0	None	No epidermal thickening
1	Mild	Minor epidermal thickening
2	Moderate	Moderate epidermal thickening; accentuated skin lines
3	Severe	Severe epidermal thickening; deeply accentuated skin lines

The EASI score will be conducted by the principal investigator or an appropriately trained designee to obtain a score to measure the extent (area) and severity of AD. EASI will be scored using the area score for each of the four regions (head and neck, trunk, upper limbs, and lower limbs) of the body. The area score is the percentage of skin affected by atopic dermatitis (eczema) for each body region:

Area score: Percentage of skin affected by eczema in each region

0	No active eczema in this region
1	1–9%
2	10–29%
3	30–49%
4	50–69%
5	70–89%
6	90–100%: the entire region is affected by eczema

At each study visit, the subject will complete the Itch Numeric Rating Score (I-NRS).

I-NRS

The subject will be asked, “How would you rate your AVERAGE itch in the past 24 hours, on a scale from 0 to 10, where 0 is No itch and 10 is Worst itch imaginable?”

Prior to morning application of the study drug, the subject will record in their diary the Worst Itch Numeric Rating Score (WI-NRS).

Each day the subject will complete the Worst-Itch Numeric Rating Score (WI-NRS).

WI-NRS

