6.3.2. Baseline Visit

If the subject is deemed eligible and proceeds to enrollment on the same day, in addition to the screening assessments the following will be conducted:

- Collect blood sample for CBC and chemistry
- Collect urine sample for urinalysis
- Assess Signs of AD prior to application of study drug
- Collect EASI score prior to application of study drug
- Collect I-NRS prior to application of study drug
- Randomize subject to study drug treatment
- Apply study drug on subject's AD lesions (see Section 5.1.5)
- Monitor subject for AEs 15 minutes after application of study drug
- Photographs and Signs of AD scoring of target lesion (selected sites only)
- Train subject in proper application of study drug
- Weigh and dispense study drug
- Dispense study diary (Day 1 through Day 28) and train the subject in entering administration times and daily pruritus score.

If the subject is not enrolled on the same day as the Screening Visit, the following will be conducted at the Baseline Visit:

- Review eligibility criteria
- Review medical history and review of systems
- Query subject for adverse events since the signing of the informed consent/assent and changes in concomitant medications
- Collect blood sample for CBC and chemistry
- Collect urine sample for urinalysis
- Conduct UPT (WOCBP only)
- Collect urine sample for UDS
- Perform IGA prior to application of study drug
- Calculate BSA of total AD involvement
- Assess Signs of AD score prior to application of study drug
- Collect EASI score prior to application of study drug
- Collect I-NRS prior to application of study drug
- Photographs and Signs of AD scoring of target lesion (selected sites only)
- Randomize subject to study drug treatment
- Apply study drug on subject's AD lesions (see Section 5.1.5)
- Monitor subject for AEs 15 minutes after application of study drug
- Train subject in proper application of study drug
- Weigh and dispense study drug

- Dispense study diary (Day 1 through Day 28) and train the subject in entering administration times and daily pruritus score.

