9.3.3. Efficacy Analyses

The efficacy variables include the IGA, BSA of AD, Signs of AD score, EASI score, and pruritus scores (I-NRS) collected at Screening/Baseline and all subsequent study visits and the WI-NRS recorded daily by subjects.

The primary efficacy endpoint for the study is the proportion of subjects with IGA success defined as an IGA score of Clear (0) or Almost Clear (1) with at least a 2-grade improvement from Baseline at Day 85. The IGA will be dichotomized into “success” and “failure” at study Day 15, Day 29, Day 57, and Day 85. Success on IGA defined as a score of Clear (0) or Almost Clear (1) and at least a 2-grade improvement from Baseline at Day 15, Day 29, Day 57, and Day 85 will be analyzed using logistic regression, adjusting for Baseline IGA.

Summary statistics will be prepared for the change from Baseline in the percent of BSA affected by AD at Days 15, 29, 57, and 85. The change from Baseline in BSA of AD will be analyzed using ANCOVA with Baseline BSA of AD and treatment as covariates.

Summary statistics will be presented for the change from baseline in each of the Signs of AD scores (erythema, exudation, excoriation, induration/papulation, and lichenification) at each timepoint (Day 15, Day 29, Day 57 and Day 85). A total score will be calculated based on the sum of each of the Signs of AD (0, 1, 2, or 3; max score of 15) and the change from baseline will be summarized for each timepoint. The change from baseline in Signs of AD score at Day 15, Day 29, Day 57, and Day 85 will be analyzed using ANCOVA with Baseline Signs of AD score and treatment as covariates.

The proportion of subjects with an EASI 50 and EASI 75 score will be summarized at Day 15, Day 29, Day 57, and Day 85 and compared using logistic regression, adjusting for Baseline EASI score. Summary statistics will be prepared for the change from Baseline in the EASI score and I-NRS at each timepoint (Day 15, Day 29, Day 57 and Day 85).

Summary statistics will be prepared for the change from Baseline in the Signs of AD score for the target lesion (selected sites) at each timepoint (Day 15, Day 29, Day 57 and Day 85).

Summaries of the pruritus scores (WI-NRS) reported by the subjects in the daily Patient Diary will be presented using daily means by treatment and with graphic presentations.

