The percent change from Baseline the EASI will be presented along with the subject's report of pruritus obtained from the Patient Diary. Time to improvement of pruritus and subject's assessment of the change in their AD from Baseline to Day 85 will be presented.

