9.3.9. Tabulation of Individual Response Data

Individual response data will be presented in data listings.

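### The SAP leaves out the protocol's EASI 75 and EASI 50 secondary endpoints and four exploratory endpoints, and its section on changes declares none of these removals

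*Protocol*

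**What the plan says.** **Protocol.** Section 3.2 and the Protocol Summary list eight secondary endpoints. The first is "The proportion of subjects with an EASI 75 score at Day 85" and the second is the EASI 50 counterpart. Section 9.3.3 plans to summarise both at Days 15, 29, 57 and 85, "compared using logistic regression, adjusting for Baseline EASI score". Table 4 schedules EASI at Baseline and those four visits. Section 9.3.3 also says that the diary WI-NRS scores "will be presented using daily means by treatment and with graphic presentations", and that time to pruritus improvement and the subject's "assessment of the change in their AD from Baseline to Day 85 will be presented". Section 9.3.9 adds: "Individual response data will be presented in data listings".

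**SAP.** Section 5.1.2 lists six secondary endpoints and section 5.1.3 lists four exploratory ones; none involves EASI, WI-NRS or subject-assessed change. Section 6.1.4 allows Baseline BSA and Baseline Signs of AD as covariates and no others. Section 6.8 names IGA, BSA, Signs of AD and I-NRS as the efficacy data to be analysed and listed. Section 8 declares four changes: Baseline IGA dropped from the IGA models, the ITT definition updated, an mITT population added, and a tipping point analysis added.

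**The concern.** A SAP may depart from its protocol, but the departure should be declared with a reason before unblinding. Protocol section 9.1 gives the SAP the role of detailing tables, listings and figures; it does not mention removing endpoints. SAP section 8 exists to record departures and is silent on these. A reader of the results could not tell a deliberate removal from an oversight and, with no EASI listing, could not derive the endpoints.

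The loss is not trivial in content. Inclusion criterion 5 fixes Baseline IGA at 3. From 3, a score of 0 or 1 is an improvement of 3 or 2 grades, so reaching 0 or 1 and improving by at least 2 grades are the same event. Barring eligibility deviations, two of the six retained secondary endpoints (SAP 6.8.2.2 and 6.8.2.3) therefore repeat the primary. EASI 75 and EASI 50 were the only secondary responder endpoints not built on the IGA.

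**Working it through.** No sample size, power or alpha figure is involved. The check is an item-by-item comparison of protocol 3.2 and 9.3.3 with SAP sections 5.1, 6.1.4, 6.8, 6.9 and 8 and the SAP indexes of tables, figures and listings.

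**Step 1: count the endpoints.**

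| Class | Protocol 3.2 | SAP 5.1.1 to 5.1.3 | Missing |
|---|---|---|---|
| Primary | 1 | 1 | 0 |
| Secondary | 8 | 6 | 8 − 6 = 2 |
| Exploratory | 8 | 4 | 8 − 4 = 4 |
| Total | 17 | 11 | 17 − 11 = 6 |

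**Step 2: compare the missing six with the declared changes.** Section 8 lists four changes, and none concerns EASI, the diary, WI-NRS or subject-assessed change. Declared: 0 of 6.

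**Step 3: see whether they appear elsewhere in the SAP.** EASI, WI-NRS and subject-assessed change are absent from the abbreviations, the methods and all three indexes. The listings numbered 16.2.6 are six: IGA, BSA, two for Signs of AD, I-NRS, and a photography log. None covers EASI or WI-NRS. The gaps in 6.1.4 and 6.8 follow from the omission and are not separate errors, but they must be changed if EASI is restored.

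**Step 4: see what data the protocol schedules for each missing endpoint.**

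| Missing endpoint | Data scheduled | Point to settle |
|---|---|---|
| EASI 75, EASI 50 | EASI at Baseline (pre-dose) and four later visits | Whether the CRF holds the total or the severity components |
| EASI change | Same | Protocol Summary: percent change at Day 85 only. Section 3.2: absolute and percent change at four visits |
| Diary pruritus change; time to a WI-NRS change of at least 4 | Daily diary WI-NRS | Which value is the reference |
| Subject-assessed change | No row in Table 4 | Whether it was collected at all |

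On EASI capture, protocol 6.1 states that "EASI will be scored using the area score for each of the four regions" and prints the 0 to 6 area scale. It also says the score measures severity, but sets out no severity scale. The CRF is not among the documents.

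On the WI-NRS reference, SAP 6.1.2 requires a Baseline value from before first application. The Baseline Visit list reads "Dispense study diary (Day 1 through Day 28) and train the subject in entering administration times and daily pruritus score". Protocol 6.1 has the diary score entered before the morning application, and 6.3.3 puts the first application in the morning. Together these may imply a Day 1 pre-dose entry, but no visit list requires one.

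**The case against.** The strongest defence is that little turns on this. The protocol (9.3.7) and the SAP (6.1.8) treat all tests as exploratory with no Type 1 error control, and protocol 9.2 disclaims hypothesis testing. Four of the six omissions are exploratory endpoints, and one of those has no scheduled collection. This stands as a limit on size: no alpha or power figure changes. It does not answer the two secondary endpoints, which the protocol defines, models and schedules, and it does not explain the silence of section 8.

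A reader might infer more than the documents support:

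- **That the SAP followed another protocol version.** Section 8 reports as an update an ITT condition that protocol 9.3.1 already has, and SAP 6.1.7 names New Zealand sites while protocol 5.1.1 describes supply to US and Australian sites. But SAP 6.4.2 also adds a requirement for at least one application, so the definition did change; 5.1.1 concerns supply and is not a list of countries. SAP 4.1.1 cites the correct protocol section for the schedule, and the dropped Baseline IGA term matches the model in protocol 9.3.3. Another version is possible but not established.
- **That the removal was selective.** Nothing shows intent, and the randomization schedule stays closed until database lock (SAP 4.1.3).
- **That the diary endpoints cannot be computed because no pre-dose WI-NRS exists.** The diary covers Day 1. Its dispensing appears after the first application in the visit list, but so does weighing and dispensing of study drug, so list order proves nothing. The position is unclear.
- **That EASI was captured as area only.** Protocol 6.1 says severity is measured as well.

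**Conclusion.** The point holds. Six of the 17 efficacy endpoints in protocol 3.2 have no analysis in the SAP: 2 of 8 secondary and 4 of 8 exploratory. None of the six is declared. Followed exactly, the SAP leaves EASI 75 and EASI 50 at Day 85 unreported without a reason. The risk is selective reporting, or the appearance of it; the primary endpoint and its analysis are untouched. The conclusion assumes that the supplied protocol, or one with the same endpoints, is in force. If a governing version removed these endpoints, the remaining defect is that the two documents need to be reconciled.

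**What to change.** Before unblinding:

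1. Reconcile the SAP with the protocol version in force. Unless that version removed them, restore EASI 75 and EASI 50 at Day 85 as secondary endpoints in SAP 5.1.2 and 6.8.2, using logistic regression on treatment and Baseline EASI. Apply the same model at Days 15, 29 and 57, as protocol 9.3.3 plans. Allow Baseline EASI in 6.1.4, add EASI to 6.8 so that the missing-data rule applies to it, and add tables and a by-subject listing. Confirm that the CRF holds the EASI total or its severity components, and state how responders are derived.
2. Settle the conflict between the Protocol Summary and section 3.2 on EASI change, then restore those summaries.
3. Restore the daily WI-NRS means and graphs, with a listing. State the reference value for diary change and for time to a change of at least 4. I-NRS cannot simply stand in, because it asks about average itch and not worst itch.
4. Declare in section 8, with the reason, every endpoint still dropped, including subject-assessed change if it was not collected.

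The cost is a version check, SAP wording, some tables and graphs, and two listings. EASI and the diary are already scheduled, and the work can be done blinded. Where the data do not support an endpoint, the cost is a reasoned entry in section 8.
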